### **3.5.4. ECG**

Single supine 12-lead ECG will be taken at all time points listed in the Schedule of Activities given in the protocol. For calculation of change from baseline for Periods 1 - 3, the baseline of Period 4 is used as post-baseline; for Period 4, the measurement on Day 3 will be used as the post-baseline measurement.

The QT, QTc, PR, QRS and heart rate will be recorded at each assessment time.

If not supplied, QTcF will be derived using Fridericia's heart rate correction formula:

$$QTcF = QT / (RR)^{1/3} \quad \text{where RR} = 60/\text{HR} \text{ (if not provided)}$$

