9.3.3.1. Electrocardiogram Analyses

Changes from baseline for the ECG parameters QT interval, heart rate, QTc interval, PR interval, and QRS complex will be summarized by treatment and time.

The number (%) of participants with maximum postdose QTc values and maximum increases from baseline in the following categories will be tabulated by treatment:

Safety QTc Assessment

Degree of Prolongation	Mild (msec)	Moderate (msec)	Severe (msec)
Absolute value	>450-480	>480-500	>500
Increase from baseline		30-60	>60

In addition, the number of participants with uncorrected QT values >500 msec will be summarized.

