### 3.4. Baseline Variables

**Start and end dates of study treatment:** The date of first dose (start date) of study treatment is the earliest date of non-zero dosing of the study drug. The date of last dose of study treatment is the latest date of non-zero dosing of the study drug.

**Definition of baseline:** For vital signs and ECG, the baseline measurement of Periods 1-3 is the last pre-dose measurement taken on Day 1 of Period 1, and the baseline measurement of Period 4 is the last pre-dose measurement taken on Day 1 of Period 4. For safety labs, the baseline measurement is the pre-dose measurement on Day -1.

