### **3.5.3. Vital Signs**

Supine blood pressure and pulse measurements will be taken at all time points listed in the Schedule of Activities given in the protocol.

For calculation of change from baseline for Periods 1 - 3, the baseline of Period 4 is used as post-baseline; for Period 4, the measurement on Day 3 will be used as the post-baseline measurement.

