## **6.6. Safety Summaries and Analyses**

A set of summary tables split by treatment will be produced to evaluate any potential risk associated with the safety and toleration of administering ritlectinib as PO solution, MR1, or MR2 formulation.

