### **6.6.2. Laboratory Data**

Laboratory data will be listed and summarized by treatment in accordance with the sponsor reporting standards. The baseline measurement is the pre-dose measurement on Day -1.

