### **6.6.4. Electrocardiograms**

For each planned time point, baseline values and change from baseline values in Periods 1-3 and Period 4 will be summarized with descriptive statistics (using sponsor default standards) as appropriate.

These data will be listed in accordance with the sponsor reporting standards. The thresholds used in the categorical summarization of vital signs data are presented in the [Appendix 1](#).

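### The SAP's single Periods 1-3 change for ECG and vital signs spans solution, MR1 and MR2, so the fasted change tables by treatment cannot be produced

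*SAP*

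**What the plan says.** **Baseline.** For ECG and vital signs, SAP 3.4 says "the baseline measurement of Periods 1-3 is the last pre-dose measurement taken on Day 1 of Period 1". Period 4 has its own Day 1 pre-dose baseline.

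**Post-baseline.** SAP 3.5.4 says "For calculation of change from baseline for Periods 1 - 3, the baseline of Period 4 is used as post-baseline", and SAP 3.5.3 has the same rule for vital signs. Both sections add "for Period 4, the measurement on Day 3 will be used as the post-baseline measurement".

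**Summaries in the SAP.** SAP 6.6.3 and 6.6.4 carry the same sentence: "For each planned time point, baseline values and change from baseline values in Periods 1-3 and Period 4 will be summarized". The lead-in to SAP 6.6 says "A set of summary tables split by treatment will be produced", and for laboratory data SAP 6.6.2 repeats this: "Laboratory data will be listed and summarized by treatment".

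**Summaries in the protocol.** Protocol 9.3.3.1 states that changes from baseline in the ECG parameters, including "QTc interval, PR interval, and QRS complex will be summarized by treatment and time". It also says that the number of participants with "maximum postdose QTc values and maximum increases from baseline in the following categories will be tabulated by treatment".

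**Status of the rule.** The SAP version history logs the period-block rule as a version 2 change. Protocol Section 9 allows the SAP to modify the protocol's plan. SAP 2.1, where such modifications are declared, reads as not applicable.

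**The concern.** The fasted change runs from before the first fasted dose to after the third. If every participant receives all three products in that interval, the change cannot say anything about one product against another.

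Vital signs and 12-lead ECG are named endpoints of the secondary objective on the safety and tolerability of MR1 and MR2. A programmer who follows SAP 3.4 to 3.5.4 could not fill the by-treatment ECG change table or the QTc-increase table of protocol 9.3.3.1 for solution, MR1 or MR2 given fasted. The Day 1 readings of Periods 2 and 3 would also enter no change score and no change-based category in SAP Appendix 1, although they are planned time points.

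A second consequence concerns early stoppers. A participant who stops before Period 4 has no Period 4 baseline and so no Periods 1-3 change, even though the Schedule of Activities provides an early-termination ECG and vital signs. SAP 5.3 refers to sponsor imputation standards that it does not reproduce.

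**Working it through.** The documents give no figure on this point to reproduce. The check is a count over the design.

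**Inputs**
- Sequences (protocol Table 2, SAP Table 2): ABC, BCA and CAB in Periods 1-3, each followed by B fed or by C fed. That is six sequences with 2 participants each, N = 12. A is solution, B is MR1, C is MR2.
- Schedule of Activities: ECG and vital signs on Day 1 of each of Periods 1-4 (pre-dose), on Day 3 of Period 4, and at early termination.
- Dosing on study days 1, 4, 7 and 10, at least 3 days apart (protocol 4.1).

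**1. What the fasted change contains.** Change = Period 4 Day 1 minus Period 1 Day 1, which is the sum of the three single-period changes. The exposure in between is A = 1, B = 1, C = 1 for all 12 completers. With identical exposure rows, the rank for treatment contrasts is 0, so no contrast among A, B and C can be estimated. Taken period by period, the same schedule gives 36 changes, 12 for each product, and contrast rank 2.

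**2. Readings used.**
- Scheduled readings after the first dose: 12 × 4 = 48.
- Used as post-baseline: Period 4 Day 1 (12) + Period 4 Day 3 (12) = 24.
- Not used in any change: Day 1 of Periods 2 and 3 = 24, and 24/48 = 50%.
- Readings that follow a fasted dose: Day 1 of Periods 2, 3 and 4 = 36, and 24/36 = 67% are unused.
- Doses with their own change score: 0 of 36 fasted, 12 of 12 fed (6 B fed, 6 C fed).

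**3. Early stopping.** Each participant who stops before Period 4 and is not replaced removes 1 of 12 (8%) from the Periods 1-3 summary.

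**4. How a by-treatment table would behave.** Let d be any shift; no size is assumed. Across the 12 participants, A is followed by B in 8, B by C in 8 and C by A in 8. Each product is the last fasted dose in 4 of 12, and precedes B fed in 2 of 6 and C fed in 2 of 6.

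*Shift only at the reading after MR2, gone by the next reading:*

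| Baseline | Solution | MR1 | MR2 | Each fed arm |
|---|---|---|---|---|
| Own period | −d × 8/12 = −0.67d | 0 | d | −d × 2/6 = −0.33d |
| Period 1 | 0 | 0 | d | 0 |

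The SAP's Periods 1-3 change shows d × 4/12 = 0.33d, with no product named.

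*Shift that starts after MR2 and persists:*

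| Baseline | Solution | MR1 | MR2 | Each fed arm |
|---|---|---|---|---|
| Own period | 0 | 0 | d | 0 |
| Period 1 | d × 8/12 = 0.67d | d × 4/12 = 0.33d | d | d |

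The SAP's Periods 1-3 change shows d, again with no product named. By symmetry the same pattern holds for a shift after A or B. Either baseline returns d for the product responsible, but each puts a different kind of shift under other products as well.

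**The case against.** **The rule was deliberate and permitted.** The version history logs it, and protocol Section 9 lets the SAP modify the plan, requiring an amendment only for major changes to the primary endpoints or their analyses. This shows intent, but it does not reconcile the current texts: protocol 9.3.3.1 still says by treatment and SAP 2.1 declares nothing.

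**SAP 6.6 is only a lead-in.** Its sentence on tables by treatment does not say every table, and the specific subsections for ECG and vital signs could be held to govern. This has force for vital signs, where the protocol makes no by-treatment promise and the conflict rests on that lead-in and on the planned-time-point wording of 6.6.3. It does not help for ECG, where protocol 9.3.3.1 is explicit.

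**The schedule is part of the cause.** Periods 1-3 have no within-period post-dose ECG or vital signs. The next reading comes at least 3 days after the dose, when protocol 4.2 expects concentrations below 5% of Cmax. This stands: no SAP wording can turn these readings into a picture of peak exposure. However, the SAP already uses one such reading, Period 4 Day 1, as post-baseline, so it has no ground for leaving out the like readings of Periods 2 and 3.

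**A by-treatment table is not clean either.** Correct, as step 4 shows, which is why both baselines are proposed.

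**Dropouts.** Protocol 4.1 allows those unrelated to safety to be replaced, so the 8% loss is certain only for safety withdrawals and unreplaced participants.

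**Other safeguards remain.** Absolute-value categories, listings, adverse event rules (Appendix 8 names a new QTcF prolongation of more than 60 ms as a possible adverse event) and the site's comparison with the current period's pre-dose ECG (protocol 8.3.3) all stay in place. They limit the harm but do not supply the promised tables.

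**Conclusion.** The concern holds. Under SAP 3.4, 3.5.3 and 3.5.4 no fasted change in ECG or vital signs can be attributed to a formulation, and the fasted by-treatment ECG tables of protocol 9.3.3.1 cannot be produced. None of the 36 fasted doses has its own change score, and 24 of 48 readings after the first dose are left out of every change. This follows from the sequences and schedule alone; the counts assume 12 completers and no effect size.

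The conflict is firm for ECG and weaker for vital signs. The impact is modest: descriptive secondary safety tables only, with no hypothesis test, and the fed changes in Period 4 remain attributable. It should be fixed because the current texts contradict each other and the remedy is cheap.

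**What to change.** In SAP 3.4, 3.5.3, 3.5.4, 6.6.3 and 6.6.4:

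1. Assign each scheduled reading after a dose to the treatment last received. That reading is the next period's Day 1 pre-dose value, Day 3 for Period 4, or the early-termination reading.
2. Summarise change and the change-based categories of Appendix 1 by treatment: A, B and C fasted (n = 12 each), B fed and C fed (n = 6 each).
3. Show change from Period 1 Day 1 pre-dose, the only drug-free Day 1 value, and also from the current period's pre-dose reading, which is the ECG baseline in protocol 8.3.3.
4. State in the report that there is one follow-up reading per dose, about 48 hours after dosing in Period 4 and at least about 3 days after in Periods 1-3. The maximum post-dose value is then that single reading, and the tables do not describe effects near peak exposure.

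If the block rule is kept instead, declare it in SAP 2.1 and reconcile it with SAP 6.6 and protocol 9.3.3.1.

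**Cost.** SAP text and table shells only. Every reading is already scheduled, so no new visit, sample or protocol amendment is needed for the by-treatment version. The downsides are two change tables instead of one, and period-specific changes that are not independent, because one reading serves as follow-up for one treatment and baseline for the next.

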### **3.5.5. Other Safety Data**

Additional safety data will be collected as described in the protocol and will be listed if collected in the sponsor's database.

## 4. ANALYSIS SETS (POPULATIONS FOR ANALYSIS)

Data for all participants will be assessed to determine if participants meet the criteria for inclusion in each analysis population prior to unblinding and releasing the database and classifications will be documented per standard operating procedures.

Population	Description	Applicable Analysis (for additional information refer to section 6)
Enrolled	“Enrolled” means a participant’s, or their legally authorized representative’s, agreement to participate in a clinical study following completion of the informed consent process and randomization.	
Full analysis set	All participants randomly assigned to study intervention and who take at least 1 dose of study intervention. Participants will be analyzed according to the product they actually received.	
Safety analysis set	All participants randomly assigned to study intervention and who take at least 1 dose of study intervention. Participants will be analyzed according to the product they actually received.	Sections 6.2, 6.5, 6.6
PK concentration	All participants who have at least 1 measurable concentration in at least 1 treatment period.	Section 6.4
PK parameter	All participants who have at least 1 PK parameter of interest (Section 3) quantified in at least 1 treatment period.	Sections 6.1, 6.2, 6.3, 6.4

### 4.1. Treatment Misallocations

All analyses will be performed on an “as-treated” basis and will not include data from participants who are randomized but not treated.

If a participant takes a treatment that is not consistent with the treatment they are randomized to, then they will be reported under the treatment that they actually receive for all safety, PK and pharmacodynamic analyses, where applicable.

### 4.2. Protocol Deviations

Participants who experience events that may affect their PK profile may be excluded from the PK analysis. At the discretion of the pharmacokineticist, a concentration value may also be excluded if the deviation in sampling time is of sufficient concern or if the concentration is anomalous for any other reason.

A full list of protocol deviations will be compiled and reviewed prior to database closure.

## 5. GENERAL METHODOLOGY AND CONVENTIONS

### 5.1. Hypotheses and Decision Rules

As this is an exploratory study, no formal hypothesis testing will be performed.

### 5.2. General Methods

Descriptive analyses will be performed. Some measures will be summarized using graphical representations by treatment, where appropriate.

For continuous variables, the data will be summarized using the number of subjects, mean, median, standard deviation, minimum, and maximum in accordance with current Pfizer's data and reporting standards. For appropriate PK parameters, geometric mean and geometric coefficient of variation (geocv%) will also be summarized. See [Section 6.4](#) for details.

For categorical or ordinal variables, number of subjects, numbers and percentages of subjects meeting the categorical criteria will be supplied in accordance with current Pfizer's data and reporting standards.

### 5.3. Methods to Manage Missing Data

For the analysis of safety endpoints, the sponsor data standard rules for imputation will be applied.

Methods to handle missing PK data are described below.

#### Concentrations Below the Limit of Quantification:

In all data presentations (except listings), concentrations below the limit of quantification (BLQ) will be set to zero. (In listings BLQ values will be reported as “<LLQ” where LLQ will be replaced with the value for the lower limit of quantification).

#### Deviations, Missing Concentrations and Anomalous Values:

In summary tables and plots of median profiles, statistics will be calculated having set concentrations to missing if 1 of the following cases is true:

1. A concentration has been collected as ND (ie not done) or NS (ie no sample),
2. A deviation in sampling time is of sufficient concern or a concentration has been flagged anomalous by the pharmacokineticist.

Note that summary statistics will not be presented at a particular time point if more than 50% of the data are missing.

### Pharmacokinetic Parameters:

Actual PK sampling times will be used in the derivation of PK parameters. If a PK parameter cannot be derived from a subject's concentration data, the parameter will be coded as NC (ie, not calculated). (Note that NC values will not be generated beyond the day that a subject discontinues). In summary tables, statistics will be calculated by setting NC values to missing; and statistics will be presented for a particular dose with  $\geq 3$  evaluable measurements.

If an individual subject has a known biased estimate of a PK parameter (due for example to an unexpected event such as vomiting before all the compound is adequately absorbed from the gastrointestinal tract), this will be footnoted in summary tables and will not be included in the calculation of summary statistics or statistical analyses.

## 6. ANALYSES AND SUMMARIES

### 6.1. Primary Endpoint(s)

- *PK parameters of ritlecitinib (fasted):  $C_{max}$ ,  $AUC_{inf}$  (if data permit), otherwise  $AUC_{last}$*

The outcomes of interest will be assessed for relative bioavailability analyses observations collected under fasted condition (in periods 1-3). These treatments are denoted by letters A, B, and C.

A = ritlecitinib 100 mg PO solution

B = ritlecitinib 100 mg (2  $\times$  50 mg) MR1 capsules

C = ritlecitinib 100 mg (2  $\times$  50 mg) MR2 capsules

Natural log transformed  $AUC_{inf}$  (if data permit),  $AUC_{last}$  and  $C_{max}$  will be analyzed using a mixed effect model with sequence, period and treatment as fixed effects and subject within sequence as a random effect. Estimates of the adjusted mean differences (Test-Reference) and corresponding 90% confidence intervals will be obtained from the model. The adjusted mean differences and 90% confidence intervals for the differences will be exponentiated to provide estimates of the ratio of adjusted geometric means (Test/Reference) and 90% confidence intervals for the ratios.

The mixed effects model will be implemented using SAS Proc Mixed, with REML estimation method and Kenward-Roger degrees of freedom algorithm. The illustrative SAS code is presented in the [Appendix 2](#).

For relative bioavailability analysis, the single dose of ritlecitinib MR1 and MR2 administered in fasted state are the Test treatments. Single dose of ritlecitinib solution under fasted condition is the Reference treatment.

Residuals from the model will be examined for normality and the presence of outliers via visual inspection of plots of residuals vs predicted values and normal probability plots of residuals but these will not be included in the clinical study report. If there are major

deviations from normality or outliers then the effect of these on the conclusions will be investigated through alternative transformations and/or analyses excluding outliers. Justification for any alternative to the planned analysis will be given in the report of the study.

A listing of the descriptive and graphical summaries for PK parameters is presented in [Section 6.4](#).

In addition, for the parameters  $AUC_{inf}$  (if data permit),  $AUC_{last}$  and  $C_{max}$ , a listing of the individual subject ratios (Test/Reference) will also be provided. Box and whisker plots for individual subject parameters ( $AUC_{inf}$ ,  $AUC_{last}$ , and  $C_{max}$ ) will be presented by treatment and overlaid with geometric means.

## 6.2. Secondary Endpoint(s)

- *PK parameters of ritlecitinib (fed):  $C_{max}$ ,  $AUC_{inf}$  (if data permit), otherwise  $AUC_{last}$*

By the design of the trial, all of the observations made in the fed state are positioned in the single treatment periods and therefore the evaluation of the food effect is potentially confounded by the period effect. We assume that the magnitude of the food effect is much larger than the magnitude of the period effect and will be able to support this assumption by estimating the magnitude of the period effect for periods 1-3 in the relative bioavailability analysis described in [Section 6.1](#).

The analysis will be based on the subset of data observed for the following MR treatments:

B = ritlecitinib 100 mg (2 × 50 mg) MR1 capsules under the fasted state  
 C = ritlecitinib 100 mg (2 × 50 mg) MR2 capsules under the fasted state

B,fed = ritlecitinib 100 mg (2 × 50 mg) MR1 capsules under the fed state  
 C,fed = ritlecitinib 100 mg (2 × 50 mg) MR2 capsules under the fed state

Natural log transformed  $AUC_{inf}$  (if data permit),  $AUC_{last}$  and  $C_{max}$  will be analyzed using a mixed effect model with sequence and treatment as fixed effects and subject within sequence as a random effect. Estimates of the adjusted mean differences (Test-Reference) and corresponding 90% confidence intervals will be obtained from the model. The adjusted mean differences and 90% confidence intervals for the differences will be exponentiated to provide estimates of the ratio of adjusted geometric means (Test/Reference) and 90% confidence intervals for the ratios.

Note that in this analysis the period is not included as a fixed effect. The mixed effects model will be implemented using SAS Proc Mixed, with REML estimation method and Kenward-Roger- degrees of freedom algorithm. The illustrative SAS code is presented in the [Appendix 2](#).

For food effect assessment, ritlecitinib MR1 and MR2 in fasted state are the Reference treatments while ritlecitinib MR1 and MR2 administered in fed state are Test treatments.

Similarly to the analysis in [Section 6.1](#), the residuals from the model will be examined for normality and the presence of outliers via visual inspection of plots of residuals vs predicted values and normal probability plots of residuals but these will not be included in the clinical study report. If there are major deviations from normality or outliers then the effect of these on the conclusions will be investigated through alternative transformations and/or analyses excluding outliers. Justification for any alternative to the planned analysis will be given in the report of the study.

A listing of the descriptive and graphical summaries for PK parameters is presented in [Section 6.4](#).

In addition, for the parameters  $AUC_{inf}$  (if data permit),  $AUC_{last}$  and  $C_{max}$ , a listing of the individual subject ratios (Test/Reference) will also be provided. Box and whisker plots for individual subject parameters ( $AUC_{inf}$ ,  $AUC_{last}$  and  $C_{max}$ ) will be presented by treatment and overlaid with geometric means.

- *Assessment of AEs, clinical laboratory tests, vital signs and 12-lead ECG*

For the secondary endpoint concerning safety, adverse events, laboratory data, vital signs, ECG data, and other safety data will be listed and summarized in accordance with the sponsor reporting standards as described in [Section 3.5](#).

### 6.3. Tertiary/Exploratory Endpoint(s)

- $T_{max}$ , and if data permit,  $T_{lag}$ ,  $CL/F$ ,  $V_z/F$ , and  $t_{1/2}$

A listing of the descriptive and graphical summaries for additional PK parameters is presented in [Section 6.4](#).

### 6.4. Descriptive and Graphical Summaries of PK Parameters

PK parameters will be collected as primary or secondary endpoints per [Section 3](#). Each PK parameter will be summarized by treatment and include the set of summary statistics as specified in the table below, where both mean and median profiles will be presented on both linear and log scales.

Parameter	Summary Statistics
$AUC_{inf}^a$ $AUC_{last}$ $C_{max}$ $CL/F^a$ $V_z/F^a$	N, arithmetic mean, median, cv%, standard deviation, minimum, maximum, geometric mean and geometric cv%.
$T_{max}$ , $T_{lag}^a$	N, median, minimum, maximum.
$t_{1/2}^a$	N, arithmetic mean, median, cv%, standard deviation, minimum, maximum.

a If data permit

Supporting data from the estimation of  $t_{1/2}$  and  $AUC_{inf}$  will be listed by treatment: terminal phase rate constant ( $k_{el}$ ); goodness of fit statistic from the log-linear regression ( $r^2$ ); the percent of  $AUC_{inf}$  based on extrapolation ( $AUC_{extrap\%}$ ); and the first, last, and number of time points used in the estimation of  $k_{el}$ . These data may be included in the clinical study report.

Presentations for rilectinib concentrations from venous blood samples will include:

- A listing of all concentrations sorted by subject ID, period and nominal time postdose. The concentration listing will also include the actual times. Deviations from the nominal time will be given in a separate listing.
- A summary of concentrations by treatment and nominal time postdose, where the set of statistics will include n, mean, median, standard deviation, coefficient of variation (cv), minimum, maximum and the number of concentrations above the lower limit of quantification.
- Median concentrations time plots (on both linear and semi-log scales) against nominal time postdose by treatment (all treatments on the same plot per scale, based on the summary of concentrations by treatment and time postdose).
- Mean concentrations time plots (on both linear and semi-log scales) against nominal time postdose by treatment (all treatments on the same plot per scale, based on the summary of concentrations by treatment and time postdose).
- Individual concentration time plots by treatment (on both linear and semi-log scales) against actual time postdose (there will be separate spaghetti plots for each treatment per scale).
- Individual concentration time plots by subject (on both linear and semi-log scales) against actual time postdose [there will be separate plots for each subject (containing all treatments) per scale].

For summary statistics, median and mean plots by sampling time, the nominal PK sampling time will be used, for individual subject plots by time, the actual PK sampling time will be used.

